11.1.1. Primary Safety and Effectiveness Endpoints

11.1.1.1. Statistical Methods

The 12-month (365-day) event/failure-free rates will be calculated using Kaplan-Meier methodology. Subjects who withdraw from the study prior to 12 months without experiencing an event will be censored on the date of withdrawal. The corresponding 2-sided 95% confidence limits will be calculated as the pointwise confidence limits using the log-log methodology.

11.1.2. Secondary Endpoints

Acute procedural success:

The percentage of Treatment subjects achieving acute procedural success will be calculated, along with the corresponding 95% 2-sided Clopper-Pearson confidence interval.

Failure-free rate at 6 months post-index procedure:

The 6-month (183-day) event/failure-free rates will be calculated using Kaplan-Meier methodology. Subjects who withdraw from the study prior to 6 months without experiencing an event will be censored on the date of withdrawal. The corresponding 2-sided 95% confidence limits will be calculated as the pointwise confidence limits using the log-log methodology.

11.2. *General Statistical Methods*

Time-to-event endpoints will be summarized using Kaplan-Meier event-free rates with 2-sided 95% pointwise log-log confidence limits. Subjects who withdraw from the study prior to 12 months without experiencing an event will be censored on the date of withdrawal.

Summary statistics will be presented for secondary and additional endpoints. E.g. event rates and confidence intervals will be provided for binary endpoints, and mean \pm SD and/or min, max, and median and quartiles will be presented for continuous endpoints.

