To collect continued effectiveness data of the Cryoablation System	Failure-free rate at 12 months including: i. failure to achieve success at index procedure, ii. documented AF/AFL/AT iii. interventions to treat these arrhythmias after blanking period, including repeated procedures cardioversion or prescription of new anti-arrhythmic drugs (or higher dose)	
Secondary		
Acute procedural success	Success of procedure (PVI)	Component of the primary effectiveness endpoint
To collect continued effectiveness data of the Cryoablation System	Failure-free rate at 6 months including failure to achieve success at index procedure, documented AF/AFL/AT or interventions to treat these arrhythmias after blanking period, including repeated procedures cardioversion or prescription of new anti-rrhythmic drugs (or higher dose)	To determine potential early benefits comparing to 12 months that has been established by the HRS consensus document.
Additional		
Quality of life assessment	Changes in the quality of life measures (AFEQT and EQ-5D-5L) between baseline and 12 months follow up	Relief from symptoms is one of the main ouotcomes reported of AF ablation

7. Study Design

The POLAR SMART study is a prospective, multicenter, single arm, post-market study.

All subjects signing the consent, undergoing the index (ablation) procedure and treated with the study devices will be followed up for one year.

7.1. *Scale and Duration*

- A minimum sample size of 200 subjects treated only with PVI is required. The maximum overall study sample size will be limited to ≤ 400 subjects.
- To avoid any center effect and bias, individual centers will not be allowed to enroll more than 20 subjects meeting enrollment criteria, unless Boston Scientific gives written approval to do so. The enrollment period is approximately 12 months.
- Approximately 30 sites in Japan and South Korea.
- Total expectation duration of study with all follow-up data collected is estimated to be approximately 36 months.
- The study duration for each subject is expected to be approximately 12 months. Each subject will be followed up at:
 - Enrollment and Baseline clinic visit, baseline visit can be the same day as enrollment visit, however the Informed Consent must be signed and dated prior to conducting any study related activities (up to 90 days before Index Procedure);
 - Index (Ablation) procedure (day 0);
 - Pre-discharge visit must be done before hospital discharge (required);

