- 12 months in-clinic follow-up visit (required);
- An additional follow-up visit is any subject visit triggered by subject symptoms, clinical events or per SOC that is not already defined as one of the study visits at the investigational site.

Table 10.1-1: Data Collection Schedule

Procedure/Assessment	Enrollment Baseline ²	Index (ablation) Procedure Day 0	Prehospital Discharge Post-Procedure before discharge	Month 3 Follow-Up (91±14 days) Clinic visit / Telephone	Month 6 Follow-Up (180±30 days) Clinic visit / Telephone	Month 12 Follow-Up (365±40 days) Clinic visit	Additional Follow-Up	Repeat (additional) ablation procedure	30-Days Safety Telephone Follow-Up (for attempt subjects only)
Informed consent process, including informed consent signature date ¹	X								
Eligibility criteria	X								
Demographics	X								
Medical history	X								
LVEF, LA diameter and LA volume	SOC ³								
Physical assessment	X		X	SOC	SOC	X	SOC		
LA assessment ⁵ imaging and thrombus assessment		SOC ⁴							
Quality of Life (AFEQT and EQ-5D-5L)	X					X			
Procedural Data		X							X ⁹
3D Mapping information		SOC							
12-Lead ECG	X ⁶	X	SOC	SOC	SOC	X	SOC	X	
Documentation of intervention for AF/AF/AT (if any)			X	X	X	X	X	X	
Documentation of new AF/AFL/AT (if any)		X	X	X	X	X	X	X	
Documentation of Medications	X	X ⁷	X ⁷	X ⁷	X ⁷	X ⁷	X ⁷	X ⁷	
Protocol deviations					X				
Adverse events assessment					X ⁸				

X = required; SOC – reporting required if done per standard of care;

- ¹ Informed Consent must be signed and dated prior to conducting any study related activities (up to 90 days before Index Procedure).
- ² Baseline visit can be the same day as enrollment visit, however the ICF must be signed before any study-related activities.
- ³ Per investigator's method. It is recommended to have the assessment within 180 days prior to enrollment.
- ⁴ Assessment of left atrium anatomy, pulmonary veins anatomy and rule-out presence of thrombus is strongly recommended and to be performed according to site's SOC practice - Assessments can be performed using CT, Magnetic Resonance Imaging (MRI), pulmonary venogram, Intracardiac Echo (ICE), Trans-Esophageal Echocardiography (TEE) or other.
- ⁵ It is recommended to have the LA assessment performed within 180 days prior to enrollment.
- ⁶ Most recent rhythm via 12-lead ECG.
- ⁷ Data will be required if there is any New, discontinued or changes to current Anti-Arrhythmic Drugs and Anticoagulation medication regimen.

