10.8. Month 6 Follow-up (180 ± 30 days)

Month 6 follow-up visit is optional, this can be either a in-clinic follow-up visit or a telephone contact follow-up as per SOC.

If any SOC clinical visit is completed either in clinic or telephone call between 150 and 210 days post-index procedure, it will qualify as a Month 6 follow-up.

Data collection during the Month 6 follow-up visit will be recorded on the respective eCRF.

Data collection includes

- Date of visit/telephone;
- Physical assessment including at minimum resting heart rate, weight, systolic and diastolic blood pressure (not required for telephone);
- Any documented recurrent AF episode(s), or new onset of AFL or AT events (≥ 30 seconds in duration from any clinical recording devices or from a 10-second 12-lead ECG);
- Any of the following interventions for AF, or new onset of AFL or ATs;
 - Repeat procedure
 - Electrical and/or pharmacological cardioversion for AF/AFL/AT
- New, discontinued or changes to current Anti-Arrhythmic Drugs and Anticoagulation medication regimen;
- Protocol deviations, if any;
- Reportable Adverse Events, including resolution of ongoing events, if applicable.
 - In cases of a pre-existing and unresolved phrenic nerve palsy the subject should be assessed to evaluate if the event resolved (method per investigator's discretion).

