10.10. Additional Visits

An additional follow-up visit is any subject visit triggered by subject symptoms that is not already defined as one of the study visits at the investigational site.

Data collection during the additional follow-up visit will be recorded on the respective eCRF.

Data collection should include:

- Date of visit;
- Physical assessment including at minimum resting heart rate, weight, systolic and diastolic blood pressure;
- Any documented recurrent AF episode(s), or new onset of AFL or AT events (≥ 30 seconds in duration from any clinical recording devices or from a 10-second 12-lead ECG);
- Any of the following interventions for AF, or new onset of AFL or ATs;
 - Repeat procedure
 - Electrical and/or pharmacological cardioversion for AF/AFL/AT
- New, discontinued or changes to current Anti-Arrhythmic Drugs and Anticoagulation medication regimen;
- Protocol deviations, if any;
- Reportable Adverse Events, including resolution of ongoing events, if applicable.
 - In cases of a pre-existing and unresolved phrenic nerve palsy the subject should be assessed to evaluate if the event resolved (method per investigator's discretion).

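### The 6-month failure-free rate is read at day 183 although no scheduled visit between the index procedure and Month 12 requires an ECG, so its level is biased upward

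*Combined protocol and SAP*

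**What the plan says.** **Estimator.** Section 11.1.2: "The 6-month (183-day) event/failure-free rates will be calculated using Kaplan-Meier methodology". The only censoring rule is: "Subjects who withdraw from the study prior to 6 months without experiencing an event will be censored on the date of withdrawal". Nothing says how to date a failure first found at a later visit, and nothing censors at the last rhythm assessment.

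**Failure window.** Under Section 6.2.3, recurrences and interventions count from Day 91 to the 6-Month follow-up; acute procedural failure counts at the index procedure.

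**Contacts and ECGs.**
- Month 3 (Section 10.7): days 77–105; a telephone call is enough.
- Month 6 (Section 10.8): "Month 6 follow-up visit is optional, this can be either a in-clinic follow-up visit or a telephone contact follow-up as per SOC". A standard-of-care contact "between 150 and 210 days post-index procedure, it will qualify as a Month 6 follow-up".
- Month 12 (Section 10.9): clinic visit required, days 325–405.
- Table 10.1-1: the 12-lead ECG is reported only if done per standard of care at pre-discharge, Month 3 and Month 6, and is required at Month 12. It is also required at a repeat ablation, which is not a scheduled visit.

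**Purpose.** Table 6.2-1 justifies the endpoint this way: "To determine potential early benefits comparing to 12 months that has been established by the HRS consensus document".

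**Additional visits.** Section 10.10: "An additional follow-up visit is any subject visit triggered by subject symptoms that is not already defined as one of the study visits". Section 10.1 is wider: "An additional follow-up visit is any subject visit triggered by subject symptoms, clinical events or per SOC". The synopsis and Section 7.1 agree with 10.1 in substance.

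**The concern.** A subject who completes the study without a Month 6 contact has no required contact on days 106–183. If the Month 3 call was made on days 77–90, there is none in the whole window from day 91 to day 183. Kaplan-Meier still carries that subject through day 183 as observed and failure-free. Suppose a recurrence begins on day 130 and causes no symptoms that prompt a visit. If the Month 12 ECG shows it, it is dated around day 365; if not, it is never counted. Either way it leaves the 6-month failures.

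This happens in completers, so better handling of withdrawals would not cure it. The reported 6-month rate would partly reflect how many sites happened to make an optional contact, which matters for a rate meant to show early benefit. The narrower sentence in Section 10.10 could add to the problem if sites follow it: routine visits outside the Month 6 window, where a silent recurrence might be found and dated, would then not be recorded as additional visits.

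**Working it through.** The plan states no expected 6-month rate, so there is no figure to reproduce.

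**1. Schedule arithmetic.**
- Days 91–183 are 93 days. Days 106–149 (44 of them) lie outside every visit window.
- The Month 6 window runs to day 210, which is 210 − 183 = 27 days past the analysis time point.

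**2. Assumed inputs.**
- True failure is 1% at day 0 (acute), 12% by day 183 and 30% by day 365. The 12% and 30% are illustrative. Section 4.1 quotes about 88% at 6 months and about 70% for another cryoballoon, and gives no time point for the 70%.
- q = share of recurrences visible only at a study contact; c = share of subjects with a Month 6 contact. The documents give neither.
- Detection at a contact is perfect, and visits are uniform in their windows.

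**3. Closed form at day 183.** With onset roughly even over the window, a silent recurrence is counted by day 183 only if there is a Month 6 contact, it falls on days 150–183, and onset came first.
- Contact by day 183: 33/60 = 0.55.
- Onset before that contact: average of 60/93 and 93/93 = 0.823.
- Product: p = 0.55 × 0.823 = 0.452.

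Reported failure (%) = 1 + 11(1 − q) + 11·q·c·p

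| q | c | Calculation | Reported (true 12.0) |
|---|---|---|---|
| 0.2 | 0.5 | 1 + 8.8 + 2.2 × 0.5 × 0.452 | 10.3% |
| 0.3 | 0.5 | 1 + 7.7 + 3.3 × 0.5 × 0.452 | 9.4% |
| 0.5 | 0.5 | 1 + 5.5 + 5.5 × 0.5 × 0.452 | 7.7% |
| 0.3 | 0 | 1 + 7.7 | 8.7% |
| 0.3 | 1 | 1 + 7.7 + 3.3 × 0.452 | 10.2% |

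A simulation with constant hazard within each period, and event-free completers censored at their Month 12 visit, gives 10.3%, 9.5% and 7.8% for the first three rows. Full Month 6 attendance does not remove the bias, because contacts on days 184–210 come too late.

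**4. Scale.** In the central case 88.0% failure-free is reported as about 90.5%, a shift of 2.5 points. With N = 200, the log-log 95% interval around 88% is 82.6% to 91.8%. The shift lies inside it, but it is systematic and does not shrink as N grows.

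**5. The 6-to-12-month difference.** The 12-month rate is read at day 365, while Month 12 visits run to day 405. Silent failures found on days 366–405 therefore fall outside the 12-month rate as well.
- Same simulation, q = 0.3, c = 0.5: reported failure is 27.3% at 12 months, and the loss from 6 to 12 months is 17.9 points (unrounded inputs) against a true 18.0.
- q = 0.5, c = 0.5: 17.6 points.
- q = 0.3, c = 0.5, with only 30% detection at contacts: about 14 points.
- A separate scenario without acute failures, true rates 80% and 70%, half of failures silent, no Month 6 contacts: 14.5 points against a true 10.0.

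The sign depends on the assumptions.

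**The case against.** **The endpoint is documented recurrence under routine care, so undocumented episodes are not failures.** This stands in part. Repeat ablations, cardioversions, drug changes and device-recorded episodes carry their own dates and can be placed correctly even if collected at Month 12. Only recurrences first seen on a visit ECG are affected. For those, the plan has no dating rule, and Kaplan-Meier treats the visit date as the event date.

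**Table 10.1-1 marks some Month 6 items as required.** The text repeatedly calls the visit optional, so the table does not create a required contact.

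**Paroxysmal episodes often end by themselves.** A silent day-130 episode may be absent from a 10-second ECG at Month 12. It is then missed at both time points rather than moved from one to the other. This is right and weakens the assumption of perfect detection, but it does not make the 6-month rate any less optimistic.

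**A reader might infer that the fall from 6 to 12 months is exaggerated.** If every Month 12 finding were dated at exactly day 365, the loss would be 30.0 − 9.5 = 20.5 points against 18.0. The documents do not support that dating: the visit window runs to day 405 and the analysis stops at day 365, so the 12-month rate rises too. Nor does Section 11 specify a 6- versus 12-month statistic, and no formal tests are planned. The comparison is a descriptive purpose in Table 6.2-1.

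**A reader might also infer that routine visits have no place to be recorded.** Only the one sentence in 10.10 is narrow. The synopsis, 7.1 and 10.1 include such visits, and Table 10.1-1 has a column for them. It is an inconsistency to reconcile, not proof that data will be lost.

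**Conclusion.** The concern holds for the level of the 6-month rate: it is biased upward whenever some recurrences that began by day 183 are first seen on a later visit ECG or not seen at all. Under the stated assumptions 12.0% failure is reported as about 9.5%, and about 7.8% to 10.3% for silent shares of 50% to 20% with half the subjects contacted at Month 6. The size rests on two shares that the documents do not give and on perfect detection at contacts; the direction does not. An effect on the 6-to-12-month difference is possible in either direction and is not established. The finding concerns a descriptive secondary rate and leaves the definition of the primary endpoint untouched. It is worth correcting because the remedy is cheap and the rate has a stated interpretive use.

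**What to change.** 1. **Section 11.1.2.** Keep Kaplan-Meier at day 183 and add a supportive interval-censored (Turnbull) 6-month estimate.
   - Interventions and device-recorded episodes keep their exact dates.
   - A recurrence first found on a visit ECG is placed between the last rhythm recording (ECG or device) showing no AF, AFL or AT and that visit. If there is no such recording after Day 91, the interval starts at Day 91. A telephone call must not start the interval, because it cannot rule out a silent recurrence.
   - Report the number of subjects with any contact on days 150–210 and, separately, with a rhythm recording in that period. Read the 6-month rate against 12 months with this caveat.
2. **Section 10.10.** Reconcile the first sentence with the definition in the synopsis, 7.1 and 10.1, so that routine visits and their dates are recorded.

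In a check of 60 simulated trials of 300 subjects (q = 0.3, c = 0.5, fixed visit days, perfect detection at contacts), mean 6-month failure was 10.1% by Kaplan-Meier and 11.4% by Turnbull against a true 11.7%. That shows what the estimator can recover under good detection. It does not test telephone contacts, and no estimator recovers episodes that are never recorded.

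Cost: some programming, one sentence in 10.10, a wider interval and a slightly less favourable 6-month rate. No visit or test is added, and Section 11.3.6 allows the change through an amended analysis plan approved before the analyses.

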11.2.1. Analysis Sets

The main analyses for all endpoints will be limited to PVI-only subjects. All available data from these subjects will be utilized. An additional summary of acute primary safety endpoint results (per Section 6.2.1) and adverse events will be provided for all Attempt subjects. Also, additional endpoint analyses may be performed on all Treatment subjects, subjects treated

with a POLARx™ FIT device, as well as subgroups of subjects who did have additional ablations beyond PVI. These subgroups include, but are not limited to:

- Subjects undergoing CTI
- Subjects undergoing CTI and other RA ablations
- Subjects undergoing LA ablations beyond just PVI.

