9.4.3. Attempt

A subject who has given written informed consent, and has any study device inserted into the body but does not receive any Cryoablation application will be classified as “ATTEMPT.” Attempts subjects will count towards the overall enrollment ceiling of 400 subjects and will be used for analysis of the endpoints as per section 11.2.1. The original signed ICF must be maintained in the center’s subject file. A subject ID will be assigned in the EDC system. These subjects won’t be allowed to be re-enrolled in the study.

Attempt subjects will be followed up to 30 days after index procedure, for safety purposes. All applicable case report forms in the EDC system will be completed. The original signed Informed Consent and any relevant documentation must be maintained in the center’s subject file.

For attempt subjects, at the minimum the following forms must be completed:

- Enrollment and Baseline eCRFs;
- Index Procedure eCRFs;
- 30 days Safety follow-up Phone Call;
- Adverse Event eCRFs or Device Deficiency eCRF for any reportable event (as defined in section 17) that occurs after signing the ICF, up to the point of subject withdrawal;
- Protocol deviation eCRF, if applicable;
- End of study eCRF.

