9.4.4. Treatment

Any subject who has given written informed consent and has the specified study device inserted into the body and received at least one Cryoablation application will be classified as “TREATMENT”. These subjects are followed in accordance with the Data Collection Schedule (Table 10.1-1) and included in all study analyses. A subject ID will be assigned in the EDC system. For TREATMENT subjects, all applicable eCRFs per the protocol will be completed. Treatment subjects do count towards the overall enrollment ceiling and will be used for analyses of the endpoints. The original signed ICF and any relevant documentation must be maintained in the center’s subject file. Treatments will be further classified into the following subgroups:

- **PVI-only:** Subjects receiving treatment for PVI only or PVI and CTI.
- **PVI plus additional ablations (PVI+):** Subjects receiving treatment for PVI (or PVI and CTI), plus additional ablations at other anatomical location(s) in the right or left atrium intended to treat AF, AT or atypical AFL.

PVI-only subjects are included in all study analyses, with additional primary endpoint analyses being performed for PVI+ subjects as well as combined PVI-only and PVI+ subjects, as described in Section [11.2.1](#).

9.5. *End-of-Study Definition*

The clinical study is considered completed when subjects are no longer being examined or the last subject’s last study visit has occurred. The subject’s end of study is defined as completion of the last visit or procedure as shown in the Data Collection Schedule (Table 10.1-1) in the study.

10. Study Methods

10.1. *Data Collection*

The data collection schedule is shown in Table 10.1-1. Data collection will take place at the following time points:

- Informed Consent and Enrollment clinic visit
- Baseline clinic visit, can be the same day as enrollment visit, however the Informed Consent must be signed and dated prior to conducting any study related activities (up to 90 days before Index Procedure);
- Index (Ablation) procedure (day 0);
- Pre-discharge visit must be done before hospital discharge (required);
- 3 months follow-up visit (recommended in-clinic follow-up visit if done as per SOC, at a minimum a telephone contact follow-up is required.) This telephone contact follow-up would only be required if in-clinic follow-up was not done.

- 6 months follow-up visit (optional, this can be either a in-clinic follow-up visit or a telephone contact follow-up as per SOC.);

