10. Confirmation of isolation of the PV at minimum by entrance block using the Cryo Mapping Catheter (Other techniques of additional assessment are per investigator's discretion) is required for all pulmonary veins or their anatomical equivalent.

Note: If at any time during the ablation procedure, the investigator is unable to continue the ablation with the designated study catheter (for the PV isolation), the investigator may complete the case with a device determined best for the subject. The case will represent an acute procedural failure (per protocol definition), regardless of PVI achievement with other catheters. The point at which failure was determined as well as the rationale (including a device deficiency or adverse event, if any) must be documented in the EDC system. A protocol deviation will be documented in the EDC system.

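### Subjects whose case ends after study-device insertion but before the first freeze are outside both the main safety rate and the acute procedural success rate, and no Attempt-inclusive rate is planned beside them

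*Combined protocol and SAP*

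**What the plan says.** Section 9.4.3 makes an Attempt of any consented subject who "has any study device inserted into the body but does not receive any Cryoablation application", whatever the reason. It adds that Attempts "will be used for analysis of the endpoints as per section 11.2.1" and that "Attempt subjects will be followed up to 30 days after index procedure, for safety purposes". Under section 9.4.4 a Treatment subject must have "received at least one Cryoablation application will be classified as" Treatment, and PVI-only and PVI+ are subgroups of Treatment.

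Section 11.2.1 then sets the analysis population: "The main analyses for all endpoints will be limited to PVI-only subjects". For the rest, a summary of acute primary safety results "and adverse events will be provided for all Attempt subjects". Section 11.1.2 names a different denominator for acute success: "The percentage of Treatment subjects achieving acute procedural success will be calculated".

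The note at the end of section 10.5.2 deals with an investigator who cannot go on with the study catheter: "The case will represent an acute procedural failure (per protocol definition), regardless of PVI achievement with other catheters". The glossary entry for primary effectiveness failure (section 23.2) is restricted to Treatment subjects.

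**The concern.** The denominator opens at the first freeze, but exposure to the study system begins before it. By the steps in section 10.5.2, the study sheath crosses the septum (step 5), the cryoablation catheter enters the left atrium (step 6), and the balloon is inflated and advanced against the vein (step 8). Freezing is step 9. The sheath is a listed system component (Table 5.1-1).

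Some acute components of the primary safety endpoint in section 6.2.1, such as tamponade or perforation, air embolism and stroke, can arise in that interval and can end the case. The endpoint covers procedure-related as well as device-related events, so its definition gives no reason to start counting at the freeze. A balloon that fails before its first use has the same consequence for acute success: the subject leaves the denominator instead of counting as a failure.

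The estimates are meant to be used. Section 7.3 gives procedural success and documentation of safety as the main goal and plans a comparison of adverse events with the literature. Section 11.3.5 plans a propensity-adjusted comparison of success with POLAR ICE. Both depend on comparable denominators.

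**Working it through.** **Who is counted where**

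| Case ends | Class | Main safety rate | Acute success | Other reporting |
|---|---|---|---|---|
| Before any study device is inserted | Intent (9.4.2) | Out | Out | No endpoint summary |
| After insertion, before first freeze | Attempt (9.4.3) | Out | Out on both denominators | Acute safety and adverse event summary (11.2.1) |
| After first freeze | Treatment (9.4.4) | In if PVI-only | In (11.1.2); in if PVI-only (11.2.1) | Full follow-up |

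The optional all-Treatment analysis in section 11.2.1 does not bring Attempts back.

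**Size.** The plan states no Attempt rate, expected event rate or precision target, so there is no figure to reproduce. From the documents: a minimum of 200 PVI-only subjects (section 7.1), Clopper-Pearson limits for acute success (section 11.1.2) and log-log limits for safety (section 11.1.1.1). Assumed: 2 acute failures and 6 safety events among the 200, and small numbers of Attempts.

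Acute success = successes / (200 + a), with all a Attempts counted as failures:

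| Attempts a | Rate | 95% limits |
|---|---|---|
| 0 | 198/200 = 99.00% | 96.43–99.88 |
| 1 | 198/201 = 98.51% | 95.70–99.69 |
| 2 | 198/202 = 98.02% | 95.01–99.46 |
| 4 | 198/204 = 97.06% | 93.71–98.91 |
| 6 | 198/206 = 96.12% | 92.49–98.31 |

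The first Attempt costs 99.00 − 98.51 = 0.49 points.

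Safety event-free rate S = 1 − (6 + b)/(200 + a), where b of the a Attempts had an acute event. Limits are S raised to exp(±1.96·se), with se = √[(1 − S)/(nS)] / |ln S| and n = 200 + a. S equals the Kaplan-Meier estimate when no one is censored before the last event.

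| a | b | S | 95% limits | Change (points) |
|---|---|---|---|---|
| 0 | 0 | 1 − 6/200 = 97.00% | 93.44–98.64 | – |
| 1 | 1 | 1 − 7/201 = 96.52% | 92.83–98.32 | −0.48 |
| 4 | 0 | 1 − 6/204 = 97.06% | – | +0.06 |
| 4 | 1 | 1 − 7/204 = 96.57% | – | −0.43 |
| 4 | 2 | 1 − 8/204 = 96.08% | 92.31–98.02 | −0.92 |
| 4 | 4 | 1 − 10/204 = 95.10% | 91.08–97.33 | −1.90 |

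In the row with 4 Attempts and 2 events, event risk goes from 3.00% to 3.92%, a ratio of 1.31. Event-free Attempts censored at about 30 days would dilute later events less than these proportions show.

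**The case against.** The strongest reply is that the safety part is already handled. The Attempt summary in section 11.2.1 is mandatory, unlike the optional subgroup analyses in the same section, so a reader can add those events back. That stands: the events leave the main rate but not the report. It does not help acute success, because the summary covers only acute safety results and adverse events.

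Several stronger readings are tempting but are not supported:

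- A reader might infer that section 9.4.3 contradicts section 11.2.1. It does not. It defers to that section, which gives Attempts an endpoint summary.
- A reader might infer that every abandoned pre-freeze case is an acute failure under section 10.5.2. The note concerns an ablation that cannot be continued with the study catheter, and the same section lists sheath and catheter insertion among the preparation steps. Only a case that fits the note, most plausibly a balloon failure during positioning, would be called a failure and yet be missing from the section 11.1.2 denominator.
- A reader might count any perforation before the freeze. Transseptal access (step 4) precedes the study sheath (step 5), so a case ended there is Intent, not Attempt, and a Treatment-plus-Attempt rate would not reach it.
- A reader might conclude that the reported safety rate is certainly too high. With no Attempt rate in the documents, neither the direction nor the size is established, since event-free Attempts move the rate slightly the other way.

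It is also fair to say that the shifts are small beside the confidence intervals and that the analysis set is pre-specified and disclosed.

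**Conclusion.** The point holds as a selective denominator. Attempts are outside the main primary safety rate and outside acute procedural success on either stated denominator, and an event or device failure in the interval between insertion and first freeze can cause that exclusion. For safety, a separate summary limits the damage; for acute success nothing does.

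The size is an illustration. It rests on 200 PVI-only subjects and assumed counts of Attempts, failures and events, and comes to about 0.5 points for each Attempt that is counted as a failure or carries an event. If there are no Attempts, nothing changes.

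This is a should-fix. The plan tests no hypothesis and states no performance goal, so the effect is on estimates and intervals, not on type I error or a pass/fail decision. The documents do not support replacing the main safety set with PVI-only plus Attempts: an Attempt has no PVI-only or PVI+ class, and some may have been planned for a roof line, so that set would mix populations.

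**What to change.** Keep the PVI-only main analysis and pre-specify beside it, in sections 11.2.1 and 11.1.2:

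1. The primary safety event-free rate in all subjects with a study device inserted (Treatment plus Attempt). Count acute events in Attempts and censor event-free Attempts at last contact, normally the 30-day call.
2. Acute procedural success in Treatment plus Attempt subjects, with Attempts counted as failures.

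Reconcile sections 10.5.2, 11.1.2 and 11.2.1 on the acute success denominator, and say whether the section 10.5.2 note applies before the first freeze. State whether acute failure in an Attempt counts toward primary effectiveness, since acute failure is a component in section 6.2.2 while the glossary limits failure to Treatment subjects.

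No new data are needed: Attempts already have index procedure and adverse event forms and the 30-day call. The cost is possibly slightly less favourable figures and a wording amendment. Any protocol amendment needs IRB/EC review under section 14.3, across approximately 30 sites.
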